6.3. RESEARCH PROCESSES

The informed consent, baseline survey and randomization will be completed in the ED by the study RA. To facilitate scheduling the coach home visits the RA will know the coach's weekly availability. For those subjects randomized to the intervention group, the RA will schedule the coach home visit within 24 hours of ED discharge ideally and then send the paramedic coach the appointment time, patient's contact information and ED discharge summary via email. To ensure that all PHI is communicated securely, UW coaches will be provided with UW Department of Medicine email addresses and at UR the coaches will also be provided with UR email addresses. Thus, all communication will be within each institution's secure, HIPAA compliant email system.

Blinded research staff will be responsible for all research surveys for the patient and caregiver. These are intended for all subjects (control and intervention group) and independent of the clinical CTI program delivered to the intervention group.

Patient subjects will be contacted four days after ED discharge. The RA will telephone the subject and complete a survey that evaluates the program fidelity and initial outcome measures (Table 2). We chose this time point because patients should have made medication changes (e.g., started an antibiotic) and contacted their provider for follow up by then. We anticipate that the survey will take no longer than 10 minutes to complete.

Patient subjects will be re-contacted thirty days after ED discharge. The RA will re-contact all subjects and complete a final survey. We anticipate that the survey will take no longer than 10 minutes to complete the telephone survey. The RA will inform subjects of the research phone numbers from which all calls will be made. It is anticipated that providing this information will re-assure subjects and give an increase sense of comfort knowing who is calling them.

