Paramedic-coached ED Care Transitions to Help Older Adults Maintain their Health								
↓ Activity → Day	0	1	2	3	4	5		30
Recruitment								
Patient and Caregiver (CG) Identified, Recruited & Randomized in ED								
Research Activities								
Control & Intervention Groups								
Patient Baseline & Follow-up Survey Calls								
CG Baseline & Follow-up Survey Calls								
Clincial Activities								
Intervention Group								
Coach Homevisit								
Coach Follow-up Patient Calls - TBD								

EFFICACY ASSESSMENTS

To evaluate the program, the RA who calls the subject will complete the following measures:

1. Care Transitions Measure: The CTM includes the 3 major domains that patients have identified as critically important to their experience with coordination out of the hospital. This will serve as a proxy measure for actual changes.
2. Medication Changes: Survey asking if medication changes are implemented (e.g., new medications started, old medications stopped). If not applicable, then that will be recorded. The date of change will also be queried.
3. Understanding of Red Flags: The discharge instructions from the ED will be abstracted for key red flags. Subjects will be asked to list the red flags for which they are monitoring their condition, and will be asked to explain the meaning of the red flag. The RA will record the subject responses verbatim. Two physicians will review the responses and score the level of understanding on a Likert scale.
4. Follow up with PCP: PCP follow up will be assessed in three different manners. The primary measure will be the time to in-person PCP follow-up (e.g., clinic or home visit). The secondary measures will be time to any PCP follow up (e.g., in-person or phone) and the third approach will be contact with PCP within the time recommended by the ED (e.g., phone or in person) follow-up.
5. Patient Self Efficacy: Wallston’s Perceived Health Competency Scale (PHCS) is a domain-specific

measure of self-efficacy. It assesses perceptions of self-efficacy specific to health-related situations but is not limited to any single behavior.

6. Patient Activation Measure: The Coleman Patient Activation Measure will be the primary measure for this assessment. A 1 point change in score is considered clinically significant for the Coleman measure.

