6.7 RETURN OF INDIVIDUAL RESEARCH RESULTS / MANAGEMENT OF HEALTH FINDINGS

As part of this study, we may identify new health information. During the consent process, we will obtain permission to disclose this information to each subject's PCP. This will be done via a template letter that will be sent by the study staff by standard postage mail to the PCP summarizing performance on the various tests. If the subject declines to allow us to provide this information to their PCP, then the disclosure will not occur.

As part of the surveys in the ED or via phone, we may identify certain findings that require physician review. For the surveys completed in the ED, the findings will be reviewed with the treating physician. For the phone surveys, these findings will be reviewed by the physicians overseeing this study at either the Rochester or Madison sites and action will be taken as clinically appropriate.

As part of the CTI coaching, the coach may identify clinical issues. Then, he/she will coach the subject to call his/her PCP to obtain further guidance. If the subject is unable to do so, then the coach will call the patient's provider or 911 for direct ED transport. By using trained providers (paramedics) with extensive clinical knowledge and having continual physician availability by phone, this decision will be maximally supported.

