9. RISK/BENEFIT ASSESSMENT

9.1 POTENTIAL RISKS

One risk involves any stress caused by the survey questions or assessments, either through the questions themselves or frustration or fatigue from completing the questions. This risk is moderate, because the questions are standard questions asked by health care providers. However, the risk can be mitigated and made less likely by taking appropriate steps described in the "Protection Against Risk" section.

Another risk involves the release of confidential information regarding the medical conditions for which subjects will be assessed and from the medical record reviews. Release of information can cause social or psychological harm. However, the risk for this is extremely unlikely due to the procedures used to mitigate this issue that are described in the "Protection Against Risk" section.

A third risk is that the study team may be able to identify issues of depression or suicidal thoughts from the surveys. Identification of these issues would require contacting appropriate individuals for intervention (e.g., your ED provider, your health care team).

A fourth risk is identification of abuse or neglect. Home visits will occur as part of this study and child abuse or neglect may be observed during a visit. We are required by state law to report this to the appropriate authorities. This may include reporting to local law enforcement or protective service agencies, resulting in legal or social risks to subjects or other members of their household.

In home visit situations where the paramedic coach identifies that a home environment requires mandatory reporting to authorities the paramedic coach will report as mandated and also communicate their findings to the study Principal Investigator (PI). Additionally, in situations where it is unclear whether mandatory reporting requirements are triggered the paramedic coach will communicate their findings to the study Principal Investigator to further discuss the case. If deemed necessary the research team will communicate concerns to the patient's primary care physician for appropriate follow-up by the PCP.

A final risk is that we may refer subjects to their primary care providers or an ED for additional care. Following these referrals will be dependent upon the subject inclination to accept the referral.

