2. The site PI designee (who must be a clinician with relevant expertise) will be notified to determine if the event is unexpected, related to participation in the research and places participants at a greater risk of physical or psychological harm than was previously known or recognized.
3. The overall PI will be notified without unblinding the PI.
4. The NIA and Independent Safety Officer will be notified within 1 business day of categorization.
5. The governing IRB will be notified within 1 business day if the SAE constitutes an UP and is immediately life-threatening or severely debilitating to other participants.
6. If it is unexpected, related, or possibly related, the other study investigators and sites will be notified promptly.
7. The PI will provide a final update to the NIA and Independent Safety Officer within 14 business days of the event for all SAE cases, unless the investigation is still ongoing.
8. The event will be discussed on the weekly study oversight call.

Grading Criteria

We will utilize the NIA approved grading criteria, as indicated on the event forms including:

Severity

- 1 = Mild- Awareness of signs or symptoms, but easily tolerated and are of minor irritant type causing no loss of time from normal activities. Symptoms do not require therapy or a medical evaluation; signs and symptoms are transient.
- 2 = Moderate- Events introduce a low level of inconvenience or concern to the participant and may interfere with daily activities, but are usually improved by simple therapeutic measures; moderate experiences may cause some interference with functioning
- 3 = Severe- Events interrupt the participant's normal daily activities and generally require systemic drug therapy or other treatment; they are usually incapacitating

Study Relatedness

- 1 = Definitely related- The adverse event is clearly related to the study procedure – i.e. an event that follows a reasonable temporal sequence from administration of the study intervention, follows a known or expected response pattern to the suspected intervention, that is confirmed by improvement on stopping and reappearance of the event on repeated exposure and that could not be reasonably explained by the known characteristics of the subject's clinical state.

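### Red-flag understanding is scored subjectively by two physicians from verbatim answers, and the plan states no masking of the scorers or of arm-revealing text

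*Combined protocol and SAP*

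**What the plan says.** Section 6.3, Efficacy Assessments, item 3 sets out the measure. Key red flags are abstracted from the ED discharge instructions, and subjects list and explain the ones they are watching for. "The RA will record the subject responses verbatim", and then "Two physicians will review the responses and score the level of understanding on a Likert scale". The two physicians are not identified. Nothing is said about masking them, about independent scoring, or about preparing the text before they see it.

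Blinding is stated for data collection, also in section 6.3: "Blinded research staff will be responsible for all research surveys for the patient and caregiver".

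Other sections bear on whether the arm could become known:

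- Section 5.2: subjects are told their allocation once the baseline survey is done.
- Section 6.1: the home visit should ideally take place within 24 to 48 hours. At that visit the coach goes over red flags and helps to build the Personal Health Record. Coaches belong to the research team.
- Section 6.7: coaches who find clinical issues are supported by "having continual physician availability by phone".
- Section 9.1: where a home raises mandatory-reporting issues, "the paramedic coach will report as mandated and also communicate their findings to the study Principal Investigator (PI"). In unclear cases, "the paramedic coach will communicate their findings to the study Principal Investigator to further discuss the case".
- Appendix A, section 1.2, on serious adverse events: "The overall PI will be notified without unblinding the PI".

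Section 12.2 analyses the Hypothesis 1A outcomes as binary, by chi-square test and logistic regression. No Likert cut-off for adequate understanding is given.

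**The concern.** A Likert rating of free text is a judgement. If the person making it can tell which subjects were coached, a slight leniency toward them looks the same as a real gain in knowledge. Blinding the interviewer does not prevent this, because the words pass unaltered to someone else.

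The text itself is the main route. A coached subject who rehearsed red flags with a paramedic a day or two before the call may mention the coach, the visit or the health record when explaining an answer. This route is open whoever the scorers are. Contact is a second route: the plan does not exclude as scorers physicians who take coach calls or take part in event review.

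At stake is the credibility of one part of Hypothesis 1A, the claim that coaching improves understanding of when to seek help.

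**Working it through.** **Step 1. Does any stated masking reach the scorers?** The plan gives no figure to reproduce on this point, so the first check is to set the sections side by side.

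| Stage | What is stated | Masked? |
|---|---|---|
| Subject gives answer | Told allocation (5.2) | No |
| Staff record answer | Blinded research staff (6.3) | Yes |
| Text prepared for scoring | Nothing beyond verbatim recording (6.3, item 3) | Not stated |
| Two physicians score | Likert scale, scorers unidentified (6.3, item 3) | Not stated |
| Overall PI, serious adverse events | To be told without unblinding (Appendix A, 1.2) | Intended, for that process |
| PI, certain home-visit findings | Told by the coach (9.1) | Arm evident, since only CTI subjects have coach visits |

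The third and fourth rows are the gap. The last two rows conflict with each other whoever scores the red flags.

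**Step 2. How much could it matter?**

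Inputs:

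- Scored per arm: 1200 × (1 − 0.25) = 900, from the recruitment target and 30-day attrition in section 12.1. Day-4 response is not given; 900 is a stand-in.
- True difference: none.
- Cut-off: at the median, so 50% of each arm is truly above it. This is assumed, because the plan gives no cut-off.
- Shift s in the scores of recognised CTI answers, toward CTI: 0.10, 0.15 or 0.20 SD (assumed).
- Fraction f of CTI answers recognised: 10%, 20%, 50% or 100% (assumed).

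A recognised answer becomes more likely to pass the cut by d = Φ(s) − 0.5:

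- s = 0.10: d = 4.0 points
- s = 0.15: d = 6.0 points
- s = 0.20: d = 7.9 points

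The apparent difference between arms is b = f × d. Its standard error is about √(2 × 0.5 × 0.5 / 900) = 2.36 points. The probability of p < 0.05, two-sided, is approximately Φ(b/SE − 1.96) + Φ(−b/SE − 1.96).

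Worked example: f = 50%, s = 0.20. Then b = 0.5 × 7.9 = 4.0 points, b/SE = 1.68, and the probability is Φ(−0.28) = 0.39.

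| Recognised CTI answers | s = 0.10 | s = 0.15 | s = 0.20 |
|---|---|---|---|
| 10% | 5.3% | 5.7% | 6.3% |
| 20% | 6.3% | 8.0% | 10.3% |
| 50% | 13.5% | 24.4% | 39.1% |
| 100% | 39% | 72% | 92% |

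The nominal rate is 5%. The bottom row is the ceiling: every CTI answer recognised and every one shifted.

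**Step 3. A second calibration.** Take the base rate of adequate comprehension as 22%, from the 78% deficient figure in section 2.2, and apply a direct shift to the whole CTI rate. With 900 per arm, the chance of a false positive favouring CTI (nominal 2.5%) is 7% for a 1-point shift, 17% for 2 points, 32% for 3 points and 69% for 5 points. The message is the same: a shift averaging 1 point does little, and one of 3 points or more does a good deal.

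**The case against.** The strongest reply is that the plan is silent on the scorers; it does not say that they work unmasked. Red-flag understanding is listed in Table 2 as a day-4 patient survey measure, and blinded staff are responsible for the surveys, so masked scoring may well be intended and a sentence simply missing. That stands as far as intent goes. It does not supply a procedure, and blinded collection leaves revealing words in the text.

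A reader might infer that the scorers are the PI or the physicians who support coaches, so that contact with coaches unmasks the scoring. The documents do not support this. The scorers are unnamed, section 6.7 does not say which physicians are on the phone, and the section 9.1 contact arises only in mandatory-reporting or unclear cases. Such contact would reveal individual subjects, not an arm. The event reviews in section 8.4 and Appendix A cover both arms, and nothing says that allocation is disclosed there.

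A reader might also take the 39% to 92% range as the expected damage. It holds only if every CTI answer is recognised. Subjects are asked to name and explain red flags, and how often they would mention a coach is unknown. At 10% recognised, the inflation is negligible.

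It is also fair to say that the importance is limited. Section 3.2 counts process measures loosely among the primary outcomes, but section 12.1 sizes the trial on repeat ED use (Hypothesis 2B), and section 12.2 reserves family-wise error control for the primary hypothesis. Red flags are only one component of Hypothesis 1A.

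Finally, Appendix A speaks of the PI's blinding in serious adverse event handling and does not declare the PI blinded throughout. The tension with section 9.1 is real, but it has no documented link to red-flag scoring and is a separate item.

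**Conclusion.** The point holds in a limited form. The plan leaves a subjective outcome open to scoring with knowledge of arm, for an unknown fraction of subjects, because it states no masking of the scorers, sets no limit on their coach contact and does not treat the text. It does not show that scoring will be unmasked.

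Under the assumptions above, the false-positive rate for this component is close to nominal if few answers are recognised (about 5% to 6% at 10%). It is materially raised at half (13.5% to 39%), and reaches 39% to 92% only in the extreme case. The shift sizes, their direction, the recognised fractions and the median cut are all assumptions, and a lower day-4 response would reduce the figures somewhat. The primary outcome, repeat ED use, is unaffected. The amendment is worth making because it is cheap and must be in place before scoring starts.

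**What to change.** Amend section 6.3, Efficacy Assessments, item 3, to state that:

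1. The two scorers are masked to arm and are chosen from physicians with no coach-support or event-review role.
2. Before scoring, a coordinator replaces references to the study coach, the study home visit or the CTI Personal Health Record with a neutral placeholder. Content that belongs to the answer stays, such as calling paramedics or 911, or a home visit by the subject's own physician. Blanket deletion of such words would remove valid responses.
3. Answers are scored by code, in random order mixed across arms, with only the abstracted ED red flags beside them.

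The same amendment could usefully set the Likert cut-off for the binary analysis, an agreement statistic and a rule for settling disagreements.

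Separately, section 9.1 (coach findings go to the PI) and Appendix A, section 1.2 (the PI hears of serious adverse events without being unblinded) must be reconciled. No escalation route is proposed here.

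The cost is protocol wording, some coordinator time on short text fields, and a restriction on who may score. No data are lost, and the sample size does not change.

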1. PROJECT SUMMARY / ABSTRACT

Older adults use the emergency department (ED) as an important source of acute care, making 20 million ED visits annually. Most older adults who visit the ED do not have conditions of sufficient severity to warrant hospital admission; thus, they are treated and discharged home. Unfortunately, older adults do poorly after being discharged home from the ED, with 20% having repeat ED visits within 30 days. The ED-to-home transition has been identified as a cause for these avoidable poor outcomes, but ED-focused interventions to improve this transition have had inconclusive outcomes and have suffered from feasibility, sustainability and scalability problems.

Coleman's Care Transition Intervention (CTI) has been **validated and is widely used** to improve the hospital-to-home transition, decreasing both hospital readmissions and costs. The CTI uses coaches, usually nurses or social workers but also lay people, to support patients who are being discharged home by transferring skills to activate patients. Applying the CTI to the ED-to-home transition is a natural extension, but it has not been evaluated in this unique and demanding setting.

In this study, **we will test our overall hypothesis that the community-based, paramedic-coordinated ED-to-home CTI will improve community-dwelling older adults' post-ED health outcomes and reduce costs.** We will evaluate CTI process outcomes by testing if participants randomized to the CTI 1) demonstrate better understanding of red flags that indicate a worsening of their condition, 2) implement required medication changes more frequently, 3) and follow up with their primary care physicians more rapidly after ED discharge, as compared to patients in the control group who receive usual care. We will also evaluate the effectiveness and cost-effectiveness of the CTI by testing if participants randomized to the CTI have 1) improved Patient Activation Measure scores 30 days after discharge, 2) have decreased frequency of ED visits, and 3) decreased health care costs within 30 days of ED discharge. To assess this, we will also measure differences in PCP, specialist, and urgent care visits. Additionally, we recognize that the CTI will not eliminate all repeat ED visits. Thus, we will identify factors independently associated with repeat ED visits among CTI recipients such that future programs can ensure their needs are adequately addressed.

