The CTI aims to improve *patient activation*, which is measured as having the skills, knowledge, and motivation to participate as effective members of the care team.⁶⁷ We will use the Wallston Perceived Health Competency Scale.

Upon study exit, we will measure our *primary outcome, health care use* within 30 days of ED discharge, through survey and administrative data from both local health systems and the insurers. We will also measure the costs of health care as well as the CTI program.

We will check the Social Security Death Index for death within 30 days for all subjects.

If a subject *withdraws* during follow-up, we will clarify the level of withdrawal that the subject is requesting—cessation of subject contact or removal from the study. If the subject requests cessation of contact, we will continue to review the subject's medical record to obtain health care use (e.g., ED use) outcomes. If a subject is *admitted to a skilled nursing facility*, which occurs in less than 2% of ED patients discharged home, we will track that outcome and measure those costs, but we will not survey those subjects.

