3.3. RATIONALE FOR INTERVENTION

We will implement and test the CTI for the intervention group because of its demonstrated effectiveness and cost-effectiveness, its applicability to the ED patient discharged home, its efficiency, particularly relating to activities in the ED, and its widespread use. We have chosen to use community-based

paramedics as the coaches for the CTI because these individuals are highly trained, available in all communities, and are highly respected by patients. Thus, paramedics are able to perform these visits in follow up to ED visits rapidly. Given that the CTI program has been tested using lay people, trained paramedics should be able to perform the required duties.

Table 2: Measures

	Measures	Time	Source/Approach
1. Demo -	Patient age, gender, marital status, race, ethnicity, education level, primary language, home ownership, living status, home address	ED	Patient survey
	Patient relationship with PCP	ED	Patient survey
	Insurance plan / number	ED	Epic review
	Primary Care Medical Home certification level	ED	Health systems
2. Clinical	New home services (since ED visit)	Day 30	Patient survey
	ED medications prior to assessment, chief complaint, final diagnosis (ICD-10), discharge medications, and instructions	ED	Epic review
	CTI Coaching & Services Forms* Personal Health Record (PHR) Home Visit/PHR Discussion Checklist Follow-up Phone Calls Checklist Patient Activation Assessment Medication Discrepancy Tool Care Transitions Measure - 3	CTI Coach home visit & coach follow up calls	CTI program records
3. Covariates	Medical history, including Charlson Comorbidity Index	ED	Patient survey
	Healthcare: Medications, home services, ED / hospital use	ED	Patient survey/ Epic review
	Health Status: Short Form-12 ⁶⁸	ED	Patient survey
	Disability Status: ADL ⁶⁹	ED	Patient survey
	Cognition: Short Blessed Test (BOMC)	ED	Patient survey
	Social Isolation: PROMIS Social isolation short form	ED	Patient survey
	Depression: PHQ-9	ED	Patient survey
	Anxiety: GAD-2	ED	Patient survey
Health literacy	ED	Patient survey	
4. Outcomes			
	Family Caregiver Activation in Transitions	ED, Day 30	Caregiver survey
	Understanding of red flags	Day 4	Patient survey
	Medication changes implemented	Day 4	Patient survey
	Follow up with PCP, specialists, urgent care	Day 4, 30	Patient survey / Epic review
	Wallston's Perceived Health Competency Scale (PHCS)	ED, Day, 30	Patient survey, Caregiver survey

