Hypothesis 2A & 2B: To evaluate difference in subjects' self-care competency, Wallston scores will be compared between intervention and control groups using the Wilcoxon Rank Sum test. Any repeat ED use and the number of ED visits during the 30-day follow up period will be compared between intervention and control groups using the Chi-square test and ANOVA as appropriate. To adjust for potential baseline differences between intervention and control subjects, a multiple logistic regression model will be constructed with repeat ED use as the dependent variable, study intervention group as the primary independent variable, and any covariates that were found to be imbalanced at baseline in our bivariate analyses. Multicollinearity between predictor variables will be assessed using multiple correlations (variance inflation factors). We will use the log likelihood ratio to assess overall model fit. We will also check for overdispersion and use Generalized Estimating Equation (GEE) to provide robust estimates of standard errors. Possible interaction effects between the covariates will be inspected and stratified analyses will be performed if there are significant interaction effects. Standard diagnostic measures for logistic regression such as Pearson residual and deviance residual will be used to check the goodness-of-fit of the regression model assumptions and identify any outliers.

Hypothesis 2C: The proposed economic assessment considers the financial costs and benefits of the CTI. Consistent with standard terminology,⁷³ we define *financial benefits* for this study as the consequences of the CTI that are related to health services cost, expenses, salaries, revenues, and other fiscal issues. It is important to recognize that adoption of the CTI will include both fixed (e.g., implementation) and variable (e.g., dependent on units of care delivered/patients served) costs. Dissemination of the program will require additional resources to cover CTI implementation. Hence, we

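### The plan names two different measures for Hypothesis 2A, and the only analysis written for it ignores the collected baseline score and gives no effect estimate

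*Combined protocol and SAP*

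**What the plan says.** Hypothesis 2A (section 2.1, repeated in 12.2) predicts higher patient activation in the intervention arm 30 days after discharge. It names no instrument. Elsewhere:

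- **Section 1 (Project Summary)** promises "improved Patient Activation Measure scores 30 days after discharge".
- **Section 3.2** introduces patient activation and then states "We will use the Wallston Perceived Health Competency Scale".
- **Section 6.3, Efficacy Assessments list**, puts Wallston under self-efficacy (item 5). Under activation (item 6) it says "The Coleman Patient Activation Measure will be the primary measure for this assessment" and adds a 1-point clinically significant change for the Coleman measure.
- **Section 12.2, Hypothesis 2A & 2B**, states "Wallston scores will be compared between intervention and control groups using the Wilcoxon Rank Sum test" and calls the construct self-care competency. The Coleman measure is not mentioned.

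On collection, Table 2 lists Wallston as an outcome in the ED and at day 30. The only patient activation form it shows is in the cell of CTI coaching forms, which includes "Patient Activation Assessment Medication Discrepancy Tool Care Transitions Measure - 3" and is completed at coach visits and calls. Section 6.3, however, says of the research surveys "These are intended for all subjects (control and intervention group)", and opens the efficacy list with "the RA who calls the subject will complete the following measures".

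On adjustment, the only adjusted model in the 2A & 2B paragraph is for the other hypothesis: "a multiple logistic regression model will be constructed with repeat ED use as the dependent variable".

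**The concern.** There are two separate problems.

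The first is which measure decides 2A. The measure called primary for activation has no analysis, and the measure that is analysed is one the protocol itself assigns to a different construct. If the two disagree at day 30, either could be reported as the activation result. It is also unclear whether the Coleman measure is collected in the control arm and at baseline. If the coaching form were its only source, there would be no control group for that comparison.

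The second is the analysis. A rank-sum test on Wallston scores does not use the ED score already collected, and the text does not say whether day-30 scores or changes are compared. It also yields a p-value with no size of effect. The plan does better for its other hypotheses: 1A and 1B get differences with 95% confidence intervals, and 1C gets a hazard ratio with one.

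**Working it through.** **Instrument, section by section**

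| Place | Measure of activation | Status of Wallston |
|---|---|---|
| Section 1 | Patient Activation Measure | not mentioned |
| Section 3.2 | Wallston | the activation measure |
| Table 2, outcomes | no patient activation row visible | outcome, ED and day 30 |
| Section 6.3, items 5 and 6 | Coleman, primary | self-efficacy |
| Section 12.2 | none analysed by that name | the only 2A analysis |

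Sections 1 and 6.3 cannot be reconciled with 3.2 and 12.2 without changing text.

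**Size of the baseline-score point**

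The plan gives no SD, effect size or power for 2A, so there is no figure of its own to reproduce.

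Inputs:
- 860 per arm, the number section 12.1 says is needed for Hypothesis 2B
- two-sided 5% and 80% power, also from 12.1
- correlation ρ between ED and day-30 Wallston: **assumed**, 0.3 to 0.7
- true shift of 0.12 SD: **assumed**

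Formulas:
- Variance of the baseline-adjusted (ANCOVA) difference relative to an unadjusted mean difference: 1 − ρ².
- Smallest difference detectable with 80% power, in SD: (1.960 + 0.842) × √(2(1 − ρ²)/n).
- Unadjusted mean comparison: 2.802 × √(2/860) = 0.135 SD.
- Wilcoxon under normality: 0.135/√(3/π) = 0.138 SD.
- Power at 0.12 SD: Φ(0.12 × √(860/2)/√(1 − ρ²) − 1.960) for ANCOVA, where 0.12 × √430 = 2.488. For Wilcoxon: Φ(2.488 × √(3/π) − 1.960) = Φ(0.472) = 68%.

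| Analysis | Variance reduction | Detectable difference (SD) | Power, formula | Power, simulated |
|---|---|---|---|---|
| Wilcoxon, as planned | – | 0.138 | 68% | 67–68% |
| ANCOVA, ρ = 0.3 | 9% | 0.129 | 74% | not run |
| ANCOVA, ρ = 0.4 | 16% | 0.124 | 77.5% | 76.8% |
| ANCOVA, ρ = 0.5 | 25% | 0.117 | 82% | 81.2% |
| ANCOVA, ρ = 0.6 | 36% | 0.108 | 87.5% | 87.6% |
| ANCOVA, ρ = 0.7 | 49% | 0.096 | 94% | 93.6% |

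The simulation used 2,000 trials per setting with normal scores. A rank-based ANCOVA kept most of the gain: 74.0%, 78.5%, 85.0% and 91.0% for ρ = 0.4 to 0.7. With ceiling-limited, skewed integer scores (range, mean and SD all assumed), the pattern was the same: Wilcoxon about 66%, ANCOVA 74%, 77%, 86% and 91%.

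Taking instead the 900 per arm left after 25% attrition (1200 × 0.75), the Wilcoxon test can detect 0.135 SD. ANCOVA can detect 0.126, 0.114 or 0.094 SD for ρ = 0.3, 0.5 or 0.7.

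**Caregiver activation (FCAT)**

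Table 2 also collects FCAT in the ED and at day 30. Section 12.2 mentions a t-test only when stating power and writes no analysis model. If 30% of 1200 patients per arm have a caregiver (section 12.2) and 25% are lost (section 12.1's patient figure, assumed to apply to caregivers), n = 1200 × 0.30 × 0.75 = 270 per arm. The detectable difference is 2.802 × √(2/270) = 0.241 SD unadjusted, and 0.221, 0.209, 0.193 or 0.172 SD adjusted for ρ = 0.4 to 0.7.

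**The case against.** The analysis section does name a measure and a test for 2A, and section 3.2 and Table 2 support it. The contrary text is one line in the summary and one item in the efficacy list. That narrows the ambiguity but does not remove it, because item 6 calls another measure primary and is current text.

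Table 2 is weak evidence that Coleman is collected only by coaches. The Care Transitions Measure sits in the same coaching cell, yet section 6.3 has the RA complete it by telephone. The table is also broken in the text available for this review. This objection stands: the fair statement is that control-arm and baseline collection are unclear, not that they are missing.

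The Wilcoxon test is valid after randomisation, so leaving out the baseline score loses precision and causes no bias. This stands too. The plan's general provisions do not fill the gap. Section 12.1 mentions site clustering in most analyses, 12.2 allows covariates in multivariable models, and the missing-data text offers weighted GEE if MCAR is severely violated. None specifies a baseline-adjusted model or an estimate for 2A.

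The size of the gain rests on assumed correlations, and at 0.3 it is modest. FCAT is a limited, added analysis, so that part is minor.

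**Conclusion.** The concern holds on both counts. The documents conflict on the instrument for Hypothesis 2A, and the measure called primary for activation has no analysis. The analysis that is written omits a baseline score already collected and specifies no effect estimate or interval.

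The conflict is a matter of text and rests on no assumption; it is the stronger reason to act. The precision loss depends on a correlation the documents do not give. Over 0.3 to 0.7 the variance saving is 9% to 49%, and power at an assumed 0.12 SD shift rises from about 68% to between 74% and 94%. Because 2A is not the powered hypothesis, neither the sample size nor the primary comparison changes. The plan should be corrected, but the trial's main conclusion does not depend on it.

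**What to change.** 1. **Fix one instrument for 2A before unblinded data are seen**, and align sections 1, 3.2, 6.3, 12.2 and Table 2.
   - If RAs collect Coleman in both arms: add it to the Table 2 outcomes with its time points, write its analysis in 12.2, and label Wallston a separate self-efficacy outcome.
   - If they do not: name Wallston as the 2A outcome, remove the sentence making Coleman primary, and reword 2A as perceived health competence.
   - In either case, state that activation forms completed by coaches are intervention-arm process data.
2. **Analyse day-30 Wallston by ANCOVA** with baseline Wallston, site and the caregiver randomisation stratum (section 5.1). Report the adjusted mean difference with its 95% confidence interval, and a rank-based ANCOVA as a sensitivity analysis. If Coleman decides 2A, use the same model with baseline Coleman if it is collected, otherwise baseline Wallston.
3. **Write the FCAT analysis** as ANCOVA on baseline FCAT and site.

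The cost is wording in sections 1, 3.2, 6.3, 12.2 and Table 2, plus Hypothesis 2A in section 2.1 if Wallston is chosen. The Wallston and FCAT models use data already planned. Choosing Wallston means the 1-point Coleman threshold, the only clinical threshold stated for 2A, no longer applies.
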